4.5. Study Treatment Exposure and Compliance Variables

Study treatment exposure variables are listed below with associated definitions:

- Patient duration of study treatment exposure in weeks defined as: (last study treatment administration date +14 first study treatment administration date)/7, regardless of intermittent discontinuations.
- The following categories will be used for treatment exposure intervals: ≥1 day and <4 weeks, ≥4 weeks and <8 weeks, ≥8 weeks and <12 weeks, ≥12 weeks and <16 weeks, ≥16 weeks and <20 weeks, ≥20 weeks and <24 weeks, ≥24 weeks and <28 weeks, ≥28 weeks and <32 weeks, ≥32 weeks and <36 weeks, ≥36 weeks and <40 weeks, ≥40 weeks and <44 weeks, ≥44 weeks and <48 weeks,, ≥188 weeks and <192 weeks, ≥192 weeks.
- The total number of study treatment injections by patient.

In addition, for patients previously exposed to PRALUENT, the combined duration of treatment will be calculated as:

 (Date of the last study medication dose in the neurocognitive function study (R727-CL-1532) – date of the first study medication dose in the neurocognitive function study (R727-CL-1532) + 14) + (Date of the last study medication dose in R727-CL-1609 [current study] – date of the first study medication dose in R727-CL-1609 [current study] + 14).

Compliance will be assessed using the following variables with associated definitions:

• For each patient, the mean injection frequency for study treatment injections will be defined as the average number of days between 2 consecutive injections, that is: (last injection date – first injection date) / (number of injections - 1) for patients receiving at least 2 injections.

All important and minor protocol deviations randomization and drug-dispensing irregularities, as well as other deviations, will be collected and reviewed on an ongoing basis throughout the study as described in the Protocol Deviation Plan (PDP). Both monitoring-collected and programmatically derived deviations are listed and defined in the PDP.

4.6. **Primary and Secondary Endpoints**

4.6.1. Primary Endpoint

The primary endpoint in the study is the incidence of AEs after first administration of study drug through the last dose of study drug plus 2 weeks.

The following AEs will be described:

- AEs/serious adverse events (SAEs)
- AEs leading to treatment discontinuation
- Adverse events of special interest (AESI)

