#### **Regeneron Pharmaceuticals, Inc.**

#### CONFIDENTIAL

Page 14 of 57

Population	
Sample Size:	Anticipated enrollment will depend on the number of patients who complete treatment in the neurocognitive function study (R727-CL-1532) and the number of patients who agree to participate (approximately 1600 patients).
Target Population:	The study population consists of patients with heFH, or non-FH patients at high or very high cardiovascular risk, who completed treatment in the neurocognitive function study (R727-CL-1532).
Treatments	
Study Drug Dose/Route/Schedule:	Sterile PRALUENT drug product will be supplied at a concentration of 75 mg/mL and 150 mg/mL in histidine, pH 6.0, polysorbate 20, and sucrose, both as 1 mL volume in an auto-injector.
	Subcutaneous injections in the abdomen, thigh or outer area of upper arm.
	75 mg Q2W or 150 mg Q2W (dose may be modified from 75 mg Q2W to 150 mg Q2W, or from 150 mg Q2W to 75 mg Q2W).
Background Treatment Dose/Route/Schedule:	Maximally-tolerated registered daily dose of statin received during the neurocognitive function study (R727-CL-1532), with or without other LMT.
	The statin dose should not be modified to adjust the degree of LDL-C lowering.
	Background LMT, including statins, should not be changed during the course of the study. However, if clinically necessary, background LMT may be adjusted at the investigator's discretion. Any adjustment will be documented in the CRF.
Endpoints	
Primary:	The primary endpoint in the study is the incidence of adverse events (AEs) after first administration of study drug through the last dose of study drug plus 2 weeks.
	The following adverse events will be described:
	• AEs/serious adverse events (SAEs)
	• AEs leading to treatment discontinuation
	• Adverse events of special interest (AESI)
Secondary:	Secondary Endpoints:
	• Calculated LDL-C values and percent changes from baseline over time
	
 
Values and percent changes from baseline in other lipids and other lipoproteins, including total cholesterol (Total-C),
 

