### 10.4.4.1. Adverse Events

### **Definitions**

For safety variables, the following observation periods are defined:

- The pretreatment period is defined as the time from signing the ICF to before the first dose of study drug.
- The TEAE period is defined as the day from first dose of study drug to the last study visit.

Pretreatment AEs are defined as those that developed, worsened, or became serious during the pretreatment period

Treatment-emergent adverse events (TEAEs) are defined as those that are not present at baseline or represent the exacerbation of a pre-existing condition during the on-treatment period.

Post-treatment AEs are defined as those that developed, worsened, or became serious during the post-treatment period.

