4.7.1. Adverse Events Variables

The period of safety observation starts from the time when the patient gives informed consent and continues into the following periods:

- The PRE-TREATMENT period: defined as the time from the signed informed consent up to the first study treatment injection.
- The treatment-emergent adverse event (TEAE) period: defined as the time from the first dose of study drug to the last study visit.
- The POST-TREATMENT period: defined as starting the day after the end of the TEAE periods up to the patient's end of study.

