4.7.1.1. Adverse Events and Serious Adverse Events

Adverse events (including serious adverse events (SAE), AEs causing permanent treatment discontinuation, deaths, and AEs of special interest) are recorded from the time of signed

informed consent until the end of study. All AEs diagnosed by the Investigator will be reported and described.

All AEs will be dictionary coded by "lowest level term (LLT)", "preferred term (PT)", "high level term (HLT)", "high level group term (HLGT)" and associated primary "system organ class (SOC)" using the version of MedDRA in effect at the time of database lock for the analysis.

Adverse Event Observation Period

- Pre-treatment AEs are AEs that developed or worsened or became serious during the pre-treatment period.
- Treatment-emergent adverse events (TEAEs) are AEs that developed or worsened or became serious during the TEAE period.
- Post-treatment AEs are AEs that developed or worsened or became serious during the post-treatment period.

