4.7.1.3. Events Causing Death

The observation periods for patient deaths are per the observation periods defined above.

- Death on-treatment: deaths occurring during the TEAE period,
- Death post-treatment: deaths occurring during the post-treatment period.

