5.7.1. Analysis of Adverse Events

In general, the primary focus of AE reporting will be on TEAEs. Pre-treatment and post-treatment AEs will be provided separately.

If an AE date/time of onset (occurrence, worsening, or becoming serious) is incomplete, an imputation algorithm will be used to classify the AE as pre-treatment, treatment-emergent, or post-treatment. The algorithm for imputing date/time of onset will be conservative and will classify an AE as treatment-emergent unless there is definitive information to determine pre-treatment or post-treatment status. Details on classification of AEs with missing or partial onset dates are provided in Section 6.4.

Adverse event incidence tables will present the number (n) and percentage (%) of patients experiencing an AE by SOC, HLGT (when applicable), HLT (when applicable), and PT. Multiple occurrences of the same event in the same patient will be counted only once in the tables within a treatment phase. For tables presenting severity of events, the worst severity will be chosen for patients with multiple instances of the same event. The denominator for computation of percentages is the safety population within each patient group.

The table of all TEAEs presented by SOC and PT will be sorted by the internationally agreed SOC order and decreasing frequency of PTs within SOCs (in the PRALUENT group). This will define the presentation order for all other tables by SOC and PT, unless otherwise specified. The tables of AEs by SOC, HLGT, HLT and PT will be sorted by the SOC internationally agreed order and the other levels (HLGT, HLT, PT) will be presented in alphabetical order, unless otherwise specified.

Analysis of all treatment-emergent adverse events

The following TEAE summaries will be generated:

- Overview of TEAEs, summarizing number (%) of patients with any
 - TEAE;
 - Serious TEAE;
 - TEAE leading to death;
 - TEAE leading to permanent treatment discontinuation.
- All TEAEs by primary SOC, HLGT, HLT, and PT
- Number (%) of patients experiencing common TEAE(s) presented by primary SOC, HLT and PT (HLT incidence ≥ 5 % in the total patient group), sorted by SOC internationally agreed order and by alphabetic order for the other levels (HLT and PT);
- All TEAEs by primary SOC and PT, sorted by the internationally agreed SOC order and by decreasing incidence of PTs within each SOC (in the PRALUENT group).

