- All TEAEs regardless of relationship in one column and, in the same table a second column with TEAEs related to alirocumab according to investigator's opinion by primary SOC, HLGT, HLT and PT;
- All TEAEs by maximal severity (i.e., mild, moderate or severe), presented by primary SOC and PT, sorted as defined above;
- The event rate per patient-year (the number of patients with an event in question divided by total patient-years) will be provided for all TEAEs by SOC and PT. For a patient with event, patient year is censored at time of first event; for patient without event, it corresponds to length of TEAE period;
- Kaplan-Meier curves will be provided, when appropriate, for time from first dose of study treatment to the first occurrence of selected TEAEs as well as incidence

rates at 48, 96, 144, and 192 weeks of exposure. Patients without any event will be censored at the end of the TEAE period. Selected TEAEs could be AESIs (e.g neurocognitive events), or TEAE related to any clinically significant signal that needs further characterization;

The frequency of selected AEs by SOC and PT over time during the treatment period (number of patients experiencing AE and percentage by patient-months) will be provided, when appropriate, by time intervals defined as: ≤48 weeks, >48 to ≤96 weeks, >96 to ≤144 weeks, >144 to ≤192 weeks, using the PROC LIFETEST with the actuarial method. Only the first event will be counted.

Analysis of all treatment emergent serious adverse event(s)

- All serious TEAEs by primary SOC, HLGT, HLT, and PT and by SOC/PT; Patient listings of serious TEAEs will be provided for the report appendix.
- All serious TEAEs regardless of relationship in one column and in the same table a second column with TEAEs related to alirocumab according to investigator's opinion, by primary SOC, HLGT, HLT, and PT;
- The event rate per patient-year will be provided for all serious TEAEs by SOC and PT.

Analysis of all treatment-emergent adverse event(s) leading to treatment discontinuation

• All TEAEs leading to permanent treatment discontinuation, by primary SOC, HLGT, HLT, and PT and by SOC/PT; Patient listings of TEAEs leading to permanent treatment discontinuation will be provided for the report appendix.

Analysis of groupings of adverse events including selected adverse events of special interest

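### The primary endpoint ends at last dose plus 2 weeks, but the planned adverse event tables use a treatment-emergent period that ends at the last study visit

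*SAP*

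**What the plan says.** The endpoint is worded consistently. The protocol synopsis gives it as the "incidence of adverse events (AEs) after first administration of study drug through the last dose of study drug plus 2 weeks". Protocol 4.2.1 and SAP 4.6.1 repeat this as the "incidence of AEs after first administration of study drug through the last dose of study drug plus 2 weeks", and list AEs and serious AEs, AEs leading to treatment discontinuation, and AEs of special interest (AESI) as the events to be described.

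The analysis period is also worded consistently, but it is a different period. Protocol 10.4.4.1: "The TEAE period is defined as the day from first dose of study drug to the last study visit". SAP 4.7.1 has the TEAE period "defined as the time from the first dose of study drug to the last study visit", with the post-treatment period starting the day after. SAP 4.7.1.1 then assigns events by period: TEAEs "are AEs that developed or worsened or became serious during the TEAE period". On-treatment deaths in SAP 4.7.1.3 are "deaths occurring during the TEAE period".

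SAP 5.7.1 builds its tables on this: "In general, the primary focus of AE reporting will be on TEAEs". For the Kaplan-Meier curves, "Patients without any event will be censored at the end of the TEAE period". Patient-years for a patient without the event equal the length of the TEAE period.

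**The concern.** AE incidence is the primary endpoint of a single-arm descriptive study, so the counting window is part of the definition of the result. If the report follows the SAP, it will state one window and tabulate another.

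The mismatch can run in either direction:

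- **Last visit before last dose plus 14 days.** Events in the gap belong to the endpoint but are left out of the TEAE tables. If captured at all, they fall into the post-treatment tables.
- **Last visit after last dose plus 14 days.** Events and person-time outside the endpoint are added.

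The sponsor ended the study early (SAP 1.1), so on-schedule completion of week 192, where the two windows nearly coincide, cannot be assumed for all patients.

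**Working it through.** **1. Is any AE summary cut at last dose plus 14 days?** Going through SAP 5.7.1 and 5.7.1.1:

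| Summary | Period used |
|---|---|
| Overview; SOC/PT; severity; relationship | TEAE period |
| Serious AEs; AEs leading to discontinuation | TEAE period |
| AESI and other groupings | TEAE period |
| Fatal AEs; deaths by period | TEAE period; post-treatment shown separately |
| Patient-year rates; Kaplan-Meier censoring | TEAE period |
| Pre-treatment and post-treatment AEs | Before first dose; after the last visit |
| Selected AEs over time, when appropriate | A treatment period that SAP 4.7.1 does not define |

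None is cut at last dose plus 14 days. The last row is optional and does not cover all AEs.

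**2. How far apart are the two end dates?** Define gap = (last study visit) − (last dose + 14 days). A positive gap means that the TEAE period is the longer one.

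Inputs: first dose is day 1 and the week 192 target is day 1345 (SAP Appendix 10.1); visit window ±3 days (protocol Table 1); dosing every 2 weeks (protocol 8.1.1, footnote 2); no dispensing at week 192 (protocol 5.1); a 192-week completer needs at least 190 weeks of exposure (SAP 4.4); exposure = (last dose + 14 − first dose)/7 (SAP 4.5).

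*Completer last dosed at week 190.* Last dose is day 7 × 190 + 1 = 1331, and 1331 + 14 = 1345. The visit falls on days 1342 to 1348. Gap = −3 to +3 days.

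*Completer at the exposure minimum.* (Last − first + 14)/7 ≥ 190 gives last − first ≥ 1316 days, so the last dose is day 1317 (week 188), and 1317 + 14 = 1331. Gap = 1342 − 1331 = +11 to 1348 − 1331 = +17 days. For an event-free patient this is 11/(1330 + 11) = 0.8% to 17/(1330 + 17) = 1.3% of TEAE time.

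*Early stopper.* Protocol 8.1.2 places the early termination visit within 1 month after the last injection, taken here as up to 30 or 31 days:

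- visit on the day of the last injection: 0 − 14 = −14 days
- visit 5 days after: 5 − 14 = −9 days
- visit 14 days after: 0 days
- visit 30 or 31 days after: +16 or +17 days

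**3. Are AEs that lead to discontinuation the same under both windows?** Not always. Protocol 8.1.1, footnote 1 treats any stop as temporary at first and ties the early termination visit to the later decision to stop permanently. An AE that starts more than 14 days after the last injection can prompt that decision. It is then in the TEAE discontinuation table but outside the endpoint. With the visit at day 31, such an AE could start in a stretch of up to 31 − 14 = 17 days.

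**4. Can the effect on incidence be computed?** No. The documents give neither event rates nor the distribution of the interval from last dose to last visit.

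**The case against.** The strongest reply is that the visit-based window is deliberate and sensible. The Amendment 2 log says that the TEAE definition was revised with the last dose and the last study visit in mind, and protocol 9.4.6 stops AE collection at that visit. On this reading the endpoint wording was simply left unaligned. This is probably what happened, and it is why restating the endpoint is an acceptable remedy. It does not remove the conflict: nothing in either document says that the TEAE period stands in for the endpoint window.

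A second reply is that the differences are days in a study planned for 192 weeks, with no test or threshold at stake. That stands, and it limits the severity.

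Some stronger readings are tempting but not supported:

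- *The SAP departed from the protocol without declaring it.* SAP 4.7.1 repeats protocol 10.4.4.1, so SAP 1.2.3 had no change of AE period to record.
- *The rule in SAP 6.3 for a missing last injection date shows that an AE cut was intended and lost.* That date has another use: the by-visit laboratory and vital-sign summaries stop at last dose plus 21 days (SAP 5.7.2 and 5.7.3).
- *The gap for early stoppers has no upper limit.* This follows only if footnote 1 of protocol 8.1.1 is read alone. A visit that also meets protocol 8.1.2 is held to about +17 days.

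**Conclusion.** The point holds and should be fixed. The stated primary endpoint and the planned AE analyses use different end dates, and no AE table computes the endpoint as written.

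The gap is −3 to +3 days for a completer last dosed at week 190, +11 to +17 days at the 190-week exposure minimum, and −14 to about +17 days for early stoppers. These figures assume dosing and visits within the protocol's rules, and a month of 30 or 31 days.

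A reader might infer that the reported incidence will be materially wrong, or biased in a known direction. The documents support neither: the gap can have either sign, and the number of patients affected is unknown. What is established is a mismatch of definition in a descriptive primary result.

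**What to change.** Use one window for the primary result, by either route.

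**(a) Keep the endpoint and add the cut.** In SAP 4.7.1 and 5.7.1, define one date: last dose in this study plus 14 days.

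- Produce the primary AE, serious AE, discontinuation, AESI and death summaries cut at that date. Apply the same date to laboratory-derived AESI (ALT elevation, and the HbA1c and glucose parts of new-onset diabetes), so that the endpoint does not mix windows.
- Keep the through-last-visit TEAE tables as supporting. They retain end-of-study samples that the cut drops.
- For all-AE and non-serious AE rates, end person-time at the earlier of last dose plus 14 days and the last visit, because AE collection stops at that visit (protocol 9.4.6).
- Footnote that serious AEs and deaths after the visit are captured only if the investigator is informed of them (protocol 9.4.2).
- Before deriving the date, correct SAP 6.3, which names the week 96 visit for completers although this study's end-of-treatment visit is week 192.

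**(b) Keep the tables and restate the endpoint.** Reword protocol 4.2.1 (with the synopsis) and SAP 4.6.1 to run from first dose through the last study visit, declare this in SAP 1.2.3, and give the last dose plus 14 days summary as a sensitivity analysis.

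Under either route, leave unchanged the tables of potentially clinically significant abnormalities and the last dose plus 21 days by-visit laboratory and vital-sign summaries. The two early termination visit timings (protocol 8.1.1, footnote 1, and 8.1.2) must be reconciled.

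The cost is one derived date and one set of AE tables under (a), or wording edits and a sensitivity summary under (b). No new data are needed. One limit remains: non-serious AEs after an early termination visit held before day 14 are not collected, so neither route recovers them.

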4.6.2. Secondary Endpoints

The secondary endpoints of the study are:

- Calculated LDL-C values and percent changes from baseline over time
- Values and percent changes from baseline in other lipids and other lipoproteins, including total cholesterol (Total-C), non-high-density lipoprotein cholesterol (non HDL-C), HDL-C, and triglycerides (TGs) over time
- Values and percent changes from baseline in gonadal hormones and gonadotropins over time: for female patients estradiol, follicle-stimulating hormone (FSH) and luteinizing hormone (LH); for male patients testosterone, FSH and LH;

4.7. Safety Variables

Patient safety will be assessed through the collection of reported adverse events (AEs), clinical laboratory data, and vital signs. Unless otherwise noted, the baseline value is defined as the last available value before the first dose study treatment.

4.7.1. Adverse Events Variables

The period of safety observation starts from the time when the patient gives informed consent and continues into the following periods:

- The PRE-TREATMENT period: defined as the time from the signed informed consent up to the first study treatment injection.
- The treatment-emergent adverse event (TEAE) period: defined as the time from the first dose of study drug to the last study visit.
- The POST-TREATMENT period: defined as starting the day after the end of the TEAE periods up to the patient's end of study.

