4.4. Patient Disposition

Patient disposition includes the description of patient status at major milestone decisions in the study, as well as the patient analysis populations.

For patient study status, the following milestone categories are defined below. For all categories of patients, percentages will be calculated using the number of enrolled patients as the denominator, with two exceptions. Specifically, the two exceptions are for the screened and non-enrolled categories, which will not have associated percentages shown.

- Enrolled patients: met the inclusion criteria regarding the target indication and signed the informed consent form (ICF)
- Enrolled but not treated patients
- Enrolled and treated patients
- Patients complete 192 weeks of open-label treatment period (at least 190 weeks of exposure and visit W192 performed)
- Patients completed the study treatment period (i.e. as collected on the End of Open-Label Treatment eCRF)
- Patients who did not complete the study treatment period and patient's decision for treatment period discontinuation (as per the End of Open-Label Treatment eCRF)
- Patients who discontinued study treatment by main reason for permanent treatment discontinuation (as per the End of Open-label Treatment eCRF)
- Patients completed the study (i.e. as collected on the Study Completion eCRF)
- Patients who early terminated the study (as per the Study Completion eCRF)
- Patients who early terminated the study by main reason for early termination (as per the Study Completion eCRF)
- Status at last study contact
- Subject's visit impact due to COVID-19
- Study/Treatment discontinuation due to COVID-19

As defined in Section 3 of this document, the patient analysis populations are:

• Safety Population (SAF)

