5.7.1.1. Patient Deaths

The following summaries of deaths will be generated.

- Number (%) of patients who died by study period (TEAE and post-treatment);
- Deaths in enrolled but not treated patients;
- TEAEs leading to death (death as an outcome on the AE CRF page, as reported by the Investigator) by (at least) SOC (sorted by internationally agreed order), and PT (sorted by decreasing frequency, showing the number (n) and percentage (%) of patients) for the safety population.

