6.3. General Missing Data Conventions

For categorical variables, patients with missing data are not included in calculations of percentages unless otherwise specified. When relevant, the number of patients with missing data is presented.

Handling of baseline definition if "time" of first study treatment administration or time of assessment at week 0 visit is missing

If the time of the first study treatment administration or the time of assessment at week 0 visit is missing, then the baseline value is defined as the last available value obtained before or on the day of the first study treatment administration.

Handling of computation of treatment duration and compliance if study treatment first or end of treatment date is missing

If the last or first injection date is missing, the exposure duration and compliance will be left as missing.

Handling of safety and efficacy analysis periods and survival analysis if end of study treatment date is missing

If the last injection date is missing, then this date is imputed to the earliest between:

- the last day of the month and year, when applicable or else the 31st of December of the year,
- the date of the end of treatment visit (week 96 visit for completer, early end of treatment visit for patients who prematurely discontinued the study treatment),
- the date of the last contact

for the purpose of safety and efficacy analysis period start and/or end.

Handling of medication missing/partial dates

No imputation of medication start/end dates or times will be performed. If a medication date or time is missing or partially missing and it cannot be determined whether it was taken prior or concomitantly, it will be considered a prior, concomitant, and post-treatment medication.

Handling of adverse events with missing or partial date/time of onset, worsening, seriousness

Missing or partial AE dates and times will be imputed so that if the partial AE date/time information does not indicate that the AE started prior to treatment or after the TEAE period, the AE will be classified as treatment-emergent. These data imputations are for categorization

purpose only and will not be used in listings. No imputation is planned for date/time of AE resolution.

Handling of adverse events when date and time of first study treatment administration is missing

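### The TEAE period closes at the last study visit, so deaths and serious events during dosing after that visit are classed as post-treatment

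*SAP*

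**What the plan says.** - **Treatment-emergent period.** SAP 4.7.1: "defined as the time from the first dose of study drug to the last study visit". Protocol 10.4.4.1 agrees: "The TEAE period is defined as the day from first dose of study drug to the last study visit". Neither names a substitute date for a patient who dies, is lost, or misses the closing visit.
- **Post-treatment period.** SAP 4.7.1: "defined as starting the day after the end of the TEAE periods up to the patient's end of study".
- **Adverse events.** SAP 4.7.1.1: "Treatment-emergent adverse events (TEAEs) are AEs that developed or worsened or became serious during the TEAE period".
- **Deaths.** SAP 4.7.1.3: "Death on-treatment: deaths occurring during the TEAE period". SAP 5.7.1.1 plans "Number (%) of patients who died by study period (TEAE and post-treatment") and restricts the table of fatal events to TEAEs.
- **Rates and curves.** In SAP 5.7.1 an event-free patient contributes the length of the TEAE period to patient-years and is censored at its end in Kaplan-Meier analyses.
- **Primary endpoint.** SAP 4.6.1 uses a different window: first administration to last dose plus 2 weeks.
- **Last contact.** In SAP 6.3, "the date of the last contact" is one of the candidate dates for imputing a missing last-injection date. It is not used to define the end of the TEAE period.
- **Missed visits.** SAP 4.4 lists "visit impact due to COVID-19" among the disposition items, so incomplete attendance was foreseen.

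**The concern.** An attended visit is a sound end point for a patient who has a week 192 or early termination visit. A patient who dies cannot attend one, and a patient who is lost does not. For these patients the only visit left to serve as the last one is an earlier scheduled visit, while dosing continued at home every 2 weeks.

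The primary objective is long-term safety, and SAP 5.7.1 makes TEAEs the main focus of adverse event reporting. A death within days of an injection that is labelled post-treatment tells the reader that it happened after drug had stopped. The same shift takes the event out of the numerator of the TEAE rates and the time after the visit out of the denominator. The tables that deliver the primary endpoint would then omit events that lie inside the endpoint's own window.

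**Working it through.** The documents state no figure on this point, so there is none to reproduce. The check sets the definitions side by side and then sizes the gap from the visit schedule.

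**1. One patient under the two windows (constructed example).** Last visit week 72, last injection week 78, serious event at week 79, death a few days later, before week 80.

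| Window | Closes at | Event at week 79 | Death |
|---|---|---|---|
| TEAE period (SAP 4.7.1, literal) | week 72 | not a TEAE | post-treatment |
| Primary endpoint (SAP 4.6.1) | week 78 + 2 = week 80 | inside | inside |

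**2. Inputs for the size.** Visits at weeks 0, 8, 12, 24, 48, 72, 96, 120, 144, 168 and 192 (SAP 2.3), so gaps of 8, 4 and 12 weeks and then seven of 24 weeks. Dosing every 2 weeks (protocol 8.1.1, footnote 2). Assumptions: deaths evenly spread over weeks 0 to 192, every scheduled visit attended, dosing on schedule until death.

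**3. Gap from last visit to death.** Mean = Σ(gap²)/2 ÷ 192 = (64 + 16 + 144 + 7 × 576)/2 ÷ 192 = 2128 ÷ 192 = 11.08 weeks, or 78 days. From week 24 on, the mean is 84 days and the maximum 168 days (24 weeks, or 12 dosing intervals).

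**4. Deaths that can count as on-treatment.** Only a death on the day of a visit qualifies: 10 ÷ 1344 days = 0.7%. Read literally, the category is almost empty by construction.

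**5. Fatal events left out of the TEAE tables.** Classification goes by onset, worsening or becoming serious, so the time from onset to death matters. The documents do not give it. For an assumed fixed lag of L days, the share with onset after the last visit is Σ max(gap − L, 0) ÷ 1344, with gaps of 56, 28, 84 and 7 × 168 days. At L = 30 this is (26 + 0 + 54 + 7 × 138) ÷ 1344 = 1046 ÷ 1344 = 78%.

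| Assumed lag (days) | 0 | 7 | 14 | 30 | 60 | 90 |
|---|---|---|---|---|---|---|
| Outside TEAE tables | 100% | 95% | 90% | 78% | 58% | 41% |
| Still a TEAE | 0% | 5% | 10% | 22% | 42% | 59% |

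This takes onset as the only trigger. An event that began before the visit stays a TEAE in any case.

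**6. Position against the primary endpoint window.** With on-schedule dosing, every such death falls within 14 days of the last dose. In 79% of them the last dose came more than 14 days after the last visit: (28 + 0 + 56 + 7 × 140) ÷ 1344 = 1064 ÷ 1344.

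**The case against.** **A closing visit may have been meant.** The last column of protocol Table 1 is the end-of-treatment, early termination or end-of-study visit, and footnote 1 makes the early termination visit the patient's last. On that reading the period does not fall back to an earlier scheduled visit; its end is simply unspecified for a patient who dies. Programmers may also intend to substitute the date of death. Both are possible, but neither is written down, and on either one the SAP still needs a rule.

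**SAP 6.3 points to dosing.** It imputes a missing last-injection date for the purpose of analysis-period limits, which suggests that a dose-based end was in mind somewhere. But it acts only when that date is missing, and 4.7.1 does not use last dose. The conservative classification in 5.7.1 and 6.3 likewise covers only incomplete event dates. An event with a known date after the last visit gets no benefit from it.

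**Not every fatal event drops out.** A reader might infer that all deaths during dosing take their fatal events out of the TEAE tables. SAP 4.7.1.1 does not support that: an event that began, worsened or became serious by the last visit stays a TEAE, and stays in the fatal-TEAE table whatever the date of death.

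**The cases are moved, not deleted.** A reader might also infer that these deaths vanish. SAP 5.7.1.1 counts deaths in both periods, and 5.7.1 plans post-treatment AE and SAE tables, so this stands against any claim of lost data. It does assume that the post-treatment period reaches the date of death; the SAP does not define the patient's end of study.

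**Lost patients matter less.** Protocol 9.4.6 collects adverse event information to the last visit. For these patients only events learned of later are affected.

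**The analyses are descriptive.** The study was terminated early and nothing is tested, so no formal decision turns on the split. That limits the consequence. But in a descriptive safety study the tables are the result.

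**Conclusion.** The point holds as a misclassification under the plan's literal wording. The TEAE period conflicts with the primary endpoint window for patients without a closing visit, and no other passage resolves it. Deaths under ongoing dosing become post-treatment deaths, except on a visit day (about 0.7% of days). Of their fatal events, between 41% and 100% fall outside the TEAE tables for assumed onset-to-death times of 90 down to 0 days; sudden events are hit hardest. These shares rest on even timing of deaths, full attendance and on-schedule dosing over the planned 192 weeks. Early termination shortens follow-up but does not change the logic.

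The number of patients affected cannot be derived, because the documents give no death rate or realised follow-up. With 1600 patients (protocol 6.1) and assumed values of 1.5 to 2.5 years and 0.5 to 1.5 deaths per 100 patient-years, total deaths would be 1600 × 1.5 × 0.005 = 12 to 1600 × 2.5 × 0.015 = 60. A reader might take that as the number misfiled. It is only an illustration of all deaths, and it does not separate those that occurred during dosing without a closing visit.

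**What to change.** In SAP 4.7.1, end the TEAE period at the later of the last study visit and last dose + 14 days, truncated at death, at least for patients without a week 192 or early termination visit. Use that date for on-treatment deaths (4.7.1.3 and 5.7.1.1) and for Kaplan-Meier censoring and patient-years (5.7.1). Reconcile it with the primary endpoint window in 4.6.1.

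The later of the two dates is needed. Protocol 8.1.1, footnote 1, treats a discontinuation as temporary at first, with visits continuing. Take a patient with a last dose at week 80 and a visit at week 96 who is then lost: a rule based on last dose + 14 days alone would stop at week 82 and drop events that are now counted. The later date keeps week 96. Under the assumptions used above, the revised rule places every death during on-schedule dosing inside the period.

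The cost is one sentence and one derivation from dates already collected. Counts of on-treatment deaths and serious TEAEs may rise slightly.
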